## DATA ANALYSIS

Once the subjects have completed the activity, the fluoroscopic videos will be stored digitally and specific frames of interest will be captured from the video and exported into the preprocessing software. The specific frames of interest will be full extension, maximum knee flexion (both inclusive), and 30° knee flexion increments during the complete flexion cycle.

Our 3D to 2D registration technique will be used to overlay the 3D models of the implanted components on their projection in the 2D fluoroscopic image. The fluoroscopic video would be digitized into frames and corrected for distortion. From here, the distortion-free images would be used with the 3D to 2D registration technique to extract *in vivo* patient femorotibial kinematics, which involves overlaying the 3D models of the components on their projection in the 2D fluoroscopic image.

Statistical analysis of the data will be carried out to analyze the two cohorts. All variables, except for lift-off and VAG, will be denoted as continuous. The data will be first checked for normality using the Shapiro-Wilk test. Only when the data is found to be normally distributed will parametric tests be used; otherwise, non-parametric tests will be used. The data will also be tested for equality of variance using the Barlett's test and Levene's test. The final selection criterion for the type of test to conduct will be based on the check for normality, as well as the check for equal variance. Therefore, for all the continuous variables, the following tests will be used:

1. Student's t-test (when the data is normally distributed and has equal variance).
2. Welch Anova test (when the data is normally distributed but has unequal variance).
3. Wilcoxon Mann Whitney U-test (when the data is not normally distributed).

Lift-off, as applicable, will be treated as a categorical variable in this study and a contingency analysis using the Fisher's exact test will be carried out. All statistical tests will be carried out at 95% confidence level ( $\alpha=0.05$ ) and will be performed using JMP® Statistical DiscoveryTM (SAS Institute Inc., Cary, NC) software.

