Kinematics in Posterior Cruciate Retaining and Bi-Cruciate Retaining Total Knee Replacements

[name].
Tennessee Orthopaedic Clinics
[name]
Knoxville, TN 37923

[name].
Erlanger Orthopaedics
[name]
Chattanooga, TN 37403

In vivo knee kinematics will be assessed for 80 subjects that have been implanted with either a Smith & Nephew Journey II posterior cruciate retaining (PCR) [40 subjects] or bi-cruciate retaining (BCR) [40 subjects] total knee arthroplasty (TKA) who are patients of [name] or [name]. Enrollment and testing will be increased to 45 patients per implant model to ensure the necessary 80 usable datasets are acquired and also to account for any subjects that may drop out of the study. All TKAs should be judged clinically successful (KSS > 80). A KSS score of greater than 90 is deemed to be excellent by the Knee Society. Each subject should have a well-functioning prosthesis, be at least three months post-operative, and should have good-to-excellent post-operative passive flexion.

Deciding which patients received which kind of implant was up to the discretion of [name] or [name], according to their professional opinions. The determination as to which type of implant patients received is outside the scope of this particular study. Subjects will already have the knee implants and must be at least three months post-operative. Bilateral subjects will not be included in the study populations.

Inclusion criteria:

1. Subjects will have either a Smith & Nephew Journey II posterior cruciate retaining (PCR) [45 subjects] or bi-cruciate retaining (BCR) [45 subjects] TKA.
2. Patients must be at least three months post-operative.
3. Participants must be judged clinically successful with their most recent new Knee Society score equal to or greater than 80.
4. Weigh < 250
5. BMI < 40
6. Must be >40 years of age
7. Participants must be able to perform the required activities without concern.
8. Subjects must be willing to sign the Informed Consent (IC) form to participate in the study.

Exclusion criteria:

1. Pregnant, potentially pregnant, lactating females or of childbearing age. To satisfy radiation protocol, each female subject will be asked if she is pregnant, or possibly could be pregnant. A pregnant person will not be allowed to participate in the study.
2. Subjects without the required type of knee implant.

3. Cannot not have pain in other parts of the body that would prohibit the patient from performing the activities

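### Lift-off is cut to a category and tested with Fisher's exact test, although the registration behind it probably yields a distance. The power lost runs from almost nothing to about 43 points, depending on the distribution.

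*SAP*

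**What the plan says.** The SAP's DATA ANALYSIS section obtains its measurements by fitting component models to fluoroscopic frames, using a "3D to 2D registration technique to extract *in vivo* patient femorotibial kinematics". The frames are full extension, maximum flexion and 30° steps between them.

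On scale it says: "All variables, except for lift-off and VAG, will be denoted as continuous". Continuous variables then go to a t-test, a Welch test or a Mann-Whitney test, depending on checks of normality and variance. Lift-off is handled separately: "Lift-off, as applicable, will be treated as a categorical variable in this study and a contingency analysis using the Fisher's exact test". The level is 0.05; sidedness is not stated.

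The available text does not say how many categories lift-off has, where the cut lies, which condyle, frame or activity counts, or why a category was chosen. It gives no unit or accuracy for separation.

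The protocol's opening section sets the size: "In vivo knee kinematics will be assessed for 80 subjects", 40 per implant. It gives no effect size, SD, lift-off rate or power.

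**The concern.** Deciding whether a condyle has lifted off means judging a gap against some limit. If the gap can be measured, a category discards its size: a 1 mm and a 4 mm separation count the same once both pass the cut. Fisher's test is also conservative at this sample size. The study could therefore miss a difference in lift-off between implants that its own rule for continuous variables would have found.

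This is a stated choice of method, so supplying the missing cut-point would not settle it. The missing detail adds a second, smaller issue: the result depends on a limit that nobody has yet fixed in writing.

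**Working it through.** **Inputs.** From the documents: 40 usable datasets per implant and alpha 0.05. Assumed: two-sided tests, one result per subject, two categories, and a difference of d = 0.634 SD, chosen because it gives a t-test 80% power at this size. The documents supply no effect size or lift-off rate.

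**The plan's own figure.** The 80 datasets cannot be reproduced, as no power inputs are given. Enrolling 45 per implant for 40 usable implies a loss of 1 − 40/45 = 11.1%; that rate is back-calculated.

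**Continuous analysis, normal shift.** Noncentrality = d × √(n/2) = 0.634 × √20 = 2.835 on 78 degrees of freedom. Power is 80.0% (Mann-Whitney about 79%).

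**Fisher's test.** If a share p0 of the reference group exceeds the cut, the other group's share is p1 = 1 − Φ(z − 0.634), where z is the 1 − p0 normal quantile. Power is the sum of Bin(a; 40, p0) × Bin(b; 40, p1) over all tables with Fisher p ≤ 0.05.

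**Floored at zero.** The same shift, but every separation below the cut counts as zero. The yes/no data, and so Fisher's power, do not change. Mann-Whitney power comes from 4,000 simulations (standard error at most √(0.25/4000) = 0.8 points).

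| p0 | p1 | Fisher | Loss against t-test (80.0%) | Mann-Whitney, floored | Loss, floored |
|---|---|---|---|---|---|
| 10% | 25.9% | 36.8% | 43.2 | about 48% | about 11 |
| 20% | 41.8% | 47.1% | 32.9 | about 61% | about 14 |
| 30% | 54.4% | 52.7% | 27.3 | about 68% | about 15 |
| 50% | 73.7% | 50.7% | 29.3 | about 73% | about 22 |

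Losses are in percentage points. Allowing for simulation error, the floored range is about 10 to 23. The actual size of Fisher's test across these rates is 1.7% to 3.3%.

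**Essentially present or absent.** With lift-off in 30% v 60% of knees and the same distribution of sizes when present, Mann-Whitney power is 73% and Fisher's 72%.

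**Raw distances with noise.** With few lift-offs (10% v 30%) and small registration noise, Mann-Whitney on unprocessed distances has 31% power against 51% for Fisher's test, because it ranks the noise among knees without lift-off. When values below the registration error were set to zero first, Mann-Whitney was 1 to 12 points above Fisher's test in every case run, with size 4% to 5%.

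**Open cut.** With no true difference, one fixed median cut gives p ≤ 0.05 in 3.4% of studies. Taking the best of three cuts gives 6.8%, and the best of five 9.7%.

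**The case against.** The strongest reply is that a distance in millimetres is never promised. The SAP speaks of kinematics and gives no unit or accuracy for lift-off. If true gaps are close to the registration error, presence or absence may be all that can be trusted. This stands as a caution. It explains why raw distances should not simply be tested, and why values below the error should become zero. It does not defend the plan as written, because the SAP neither gives this reason nor states an error.

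A second reply is that normal data are the wrong model for a quantity that cannot fall below zero. This also stands, and it cuts the loss to about 10 to 23 points or less. A well-placed cut can even match the rank test: in one simulated case (lift-off in 30% v 50%, with larger gaps in the second group) a cut at 1 unit gave Fisher's test 71% power against 70% for Mann-Whitney, but a cut at zero gave 38%. That advantage needs the right cut to be known beforehand.

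Third, a subject's maximum separation is a poor summary if frame counts differ. Subjects who flex further contribute more 30° steps, and the expected maximum of pure independent normal noise rises from 1.03 SD with 4 frames to 1.17 with 5 and 1.27 with 6. This stands too, and a fixed common set of frames answers it.

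A reader might infer that frames will be pooled as if they were independent subjects, or that the cut will be picked after the data are seen. The SAP says neither. One result per subject is equally a condition of the t-test and the Mann-Whitney test, and the error rates for several cuts show only what an unfixed cut would permit.

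**Conclusion.** The concern holds, with a size that depends on assumptions. The SAP takes lift-off out of the continuous variables and gives it a test that usually has less power than one it already names. At 40 per implant the loss is about 27 to 43 points for a pure normal shift of 0.634 SD with reference lift-off rates of 10% to 50%, about 10 to 23 points if separation is floored at zero, and close to nil if gaps hardly vary in size.

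A reader might shorten this to a loss of up to half the power. The documents support no such figure, and it is not a ceiling. Under the normal model, 36.8% against 80.0% is already a relative loss of 1 − 36.8/80.0 = 54%, and with 10% of all subjects above the cut Fisher's power falls to 19.9%, a relative loss of 75%. Under other distributions the loss nearly vanishes.

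Lift-off is not named as a primary endpoint, and Fisher's test on a defined category is valid. This is a change worth making; it does not undermine the study.

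**What to change.** In the SAP's DATA ANALYSIS section:

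1. Define lift-off: the condyle or condyles, the activities, and a fixed set of flexion frames common to all subjects.
2. For each subject and activity, take one separation value over those frames.
3. State the registration error and its source before analysis, and set separations below it to zero.
4. Compare the implants with the Mann-Whitney test the SAP already names.
5. Report yes/no lift-off at the same pre-fixed cut with Fisher's test as a supplement, one result per subject and activity.

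If the registration cannot give a usable distance, say so, and state the categories and the cut with their reason.

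The cost is SAP wording plus one figure that the documents do not contain: the registration error, from the group's own validation. No further imaging or subjects are needed. The gain is small if separations hardly vary in size.
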